#### Primary analysis of secondary endpoints

The secondary outcome time to death will be evaluated using Cox proportional-hazards regression. Other secondary time-to-event outcomes will be analysed using competing risk models as described above. Binary outcomes will be analysed using logistic regression, All models will be adjusted for the frequency of monitoring (protocolled vs standard).

CTU Bern	Statistical Analysis Plan ImaCorll	Date effective: 2018-04-24		
CTO Bern	Based on CS_STA_TEM-11_SAPtemplate_v01			Page 13 I 16

### 9.5.2. Secondary comparison between protocolled vs standard monitoring frequency

Second, we will test the secondary hypothesis, the difference in time to resolution of circulatory shock between the protocolled and standard frequency monitoring group, adjusted for the method of monitoring.

We will analyse primary and secondary endpoints as described above. All models will be adjusted for the method of monitoring (hTEE vs standard).

We will also test for an interaction between the method (hTEE vs standard) and frequency of hemodynamic monitoring (protocolled vs standard) in order to assess if effects are different depending on the method and frequency of monitoring, entering an interaction term in the models described above.

#### 9.6. Secondary analyses

Secondary analyses will include a per-protocol analysis as well as sensitivity analyses.

First, we will perform a per-protocol analysis based on the per-protocol analysis set.

Second, we will evaluate the primary endpoint censoring after 3 days and after 28 days using the FAS.

Finally, we will perform subgroup analysis for the method (hTEE vs. standard monitoring) and the frequency (per protocol vs. standard interval) of hemodynamic monitoring using the FAS.

#### 9.7. Evaluation of safety parameters

All safety analyses will be performed using the Safety Set.

SAEs will be deemed treatment emergent if the onset date is on or after the date of first study treatment. SAEs will be summarized by presenting for each treatment arm the total number of any SAE, the total number of any SAE by type, and the number and percentage of patients having any SAE, and any SAE type. Only SAEs that might be treatment related were collected and will be reported.

All other information collected (e.g., severity or relationship to study treatment) will be tabulated and listed as appropriate.

#### 9.8. Interim analyses

No interim analysis is planned.

CTU Bern	Born Statistical Analysis Plan ImaCorII Date effectiv		2018-04-24	
CTO Bern	Based on CS_STA_TEM-11_SAPtemplate_v01			Page 14 I 16

#### 9.9. Methods for handling missing data

The primary outcome is a time to event outcome. Thus, data in the primary outcome will be censored if a patient is lost to follow-up (e.g. discharged before reaching the primary endpoint). Secondary time-to-event outcomes will be handled likewise. Missing binary data will be assumed as being absent. For the descriptive analysis of continuous outcomes, an available case analysis will be performed.

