#### 7.3. Data preparation

The primary endpoint will be derived as the difference in hours between the date and time of randomization and the date and time of resolution of clinical shock. The competing risk of death for the primary outcome will be derived as the difference in hours between the date and time of randomization and the date and time of discontinuation of therapy before death.

Secondary and further endpoints will be derived as follows:

- Time to death (in hours) will be derived as the difference in hours from randomization to discontinuation of therapy before death.
- Time to resolution of clinical signs of shock will be derived as the difference in hours from randomisation to the latest time of any of the three: first lactate below 2 mmol/L, urine output above 0.5 ml/kg body weight or first capillary refilling time below three seconds
- Pulmonary artery catheter is yes if it was yes during any assessment
- Central venous catheter is yes if it was yes during any assessment
- Conventional echocardiography will be regarded as yes if TEE or TTE was used during any assessment
- Cardiac arrhythmias will be derived from any non sustained ventricular tachycardia (≥ 4 beats), sustained ventricular tachycardia, ventricular fibrillation, atrial fibrillation, atrial flutter, other supraventricular tachycardia, new onset AV block (I/II/III), or asystole
- myocardial infarction, skin necrosis, and stroke will be taken as is
- secondary bowel or limb ischemia will be derived from any bowel ischemia or any limb ischemia
- secondary infections will be derived from any catheter infection, VAP infection or sepsis
- Length of time with organ support (in hours) will be derived from length of time with mechanical ventilation and/or renal replacement therapy. If a patient received both, times will be added. If therapies are overlapping, time will only be counted once.
- Length of time in ICU (in hours) will be taken from eCRF as is.
- Length of time in hospital (in hours) will be taken from eCRF as is.

CTU Bern			2018-04-24
CTO Bern	Based on CS_STA_TEM-11_SAPtemplate_v01		Page 10 I 16

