#### Primary analysis of primary endpoint

The analysis of the primary endpoint will be a superiority analysis based on the full analysis set, asking whether hTEE monitoring is superior in time to resolution of circulatory shock as compared to standard monitoring. We will use a Fine-Gray competing risk regression model accounting for the competing risk of death (Fine and Gray 1999), adjusted for the frequency of monitoring (protocolled vs standard).

The primary outcome will be censored after 6 days in the primary analysis, because continuous hTEE monitoring was only continued for 72h after randomisation. Patients which were discharged without reaching the primary endpoint before 6 days will be censored as well. The strength of the association between each covariate and the outcome is reflected by the sub-hazard ratio in these competing risks models. The sub-hazard ratio is the ratio of the hazard associated with the cumulative incidence function under different values of the covariate, taking into account the hazard of the competing event (death).

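### The censoring rule in SAP 9.9, written for the primary outcome, carries over to time to death without a stated horizon, and 7.3 leaves some deaths undated

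*SAP*

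**What the plan says.** **Censoring.** SAP 9.9 says the primary outcome is "censored if a patient is lost to follow-up (e.g. discharged before reaching the primary endpoint"), and then "Secondary time-to-event outcomes will be handled likewise". Section 9.5.1 also makes discharge a reason to censor the primary outcome: "Patients which were discharged without reaching the primary endpoint before 6 days will be censored as well". Time to death is the first secondary endpoint in 6.2. No section exempts it.

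**Model and horizon.** Section 9.5.1 states: "The secondary outcome time to death will be evaluated using Cox proportional-hazards regression". No end of follow-up is given. The next sentence, "Other secondary time-to-event outcomes will be analysed using competing risk models as described above", covers only the other endpoints. The 6-day limit in 9.5.1 is written for the primary outcome, and so are the further limits in 9.6: "we will evaluate the primary endpoint censoring after 3 days and after 28 days using the FAS". Section 9.5.2 reuses the same models for the frequency comparison.

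**Date of death.** Section 7.3 says: "Time to death (in hours) will be derived as the difference in hours from randomization to discontinuation of therapy before death". The competing event of the primary outcome is timed the same way, between the "date and time of randomization and the date and time of discontinuation of therapy before death".

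**Origin of the endpoint.** Section 10 records that time to death replaced ICU and hospital death as a secondary endpoint. Those two remain in 6.3 as descriptive outcomes.

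**The concern.** Discharge is a sensible reason to stop observing the primary outcome, which needs blood pressure readings every 1 to 2 minutes. It is not a natural reason to stop observing survival. Patients who leave alive are generally those who are recovering, so censoring them makes the remaining risk set progressively sicker. If hTEE shortens shock, as the trial hopes, hTEE patients may also leave sooner. Their risk set would then become sicker faster, which pushes the hazard ratio up, against hTEE, with no true difference in mortality.

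The hazard ratio for time to death is likely to be read as the trial's mortality result. As written, two analysts could follow the SAP and report different numbers: one for death before discharge, the other for death up to whatever date vital status is known. The trial is open-label and the statistician is not blinded (4.4), so the choice should be fixed beforehand.

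The dating rule is a separate matter. A patient who dies without therapy having been discontinued has no defined event time, either for this endpoint or as a competing event in the primary Fine-Gray model.

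**Working it through.** **1. The text.** The SAP gives no figure to reproduce for this point. Side by side: 9.9 has a rule (censor when lost), an example (discharge) and an extension (all secondary time-to-event outcomes). Sections 9.5.1 and 9.6 contain three horizons (3, 6 and 28 days), none of them attached to time to death. Section 7.3 has one date rule, which presupposes that therapy was discontinued. Section 9.9 does not say whether discharge means from the ICU or from hospital.

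**2. Inputs for the size of the effect.** Apart from the 4.5 h saving, all are assumptions.
- 250 patients per monitoring arm (from 4.2: 125 in each of four groups).
- 25% dead by day 28 (672 h); varied from 15% to 35%.
- Median time to discharge 96 h; varied from 48 to 240 h.
- Severity Z, normal with mean 0 and SD 0 to 2. Death hazard = a·exp(Z), discharge hazard = b·exp(−Z), both constant in time. Discharge does not change the death hazard.
- Earlier discharge with hTEE: 4.5 h (18.5 − 14.0 in 4.2, assuming the whole saving in shock time passes to discharge), 10%, or 25% (24 h of 96 h).

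**3. Bias when the true hazard ratio is 1.00.** Large-sample Cox hazard ratio for arm, censored at discharge:

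| hTEE discharge | SD 0 | SD 0.5 | SD 1 | SD 1.5 | SD 2 |
|---|---|---|---|---|---|
| Same timing | 1.00 | 1.00 | 1.00 | 1.00 | 1.00 |
| 4.5 h earlier | 1.00 | 1.00 | 1.02 | 1.02 | 1.02 |
| 10% earlier | 1.00 | 1.02 | 1.03 | 1.03 | 1.03 |
| 25% earlier | 1.00 | 1.05 | 1.09 | 1.09 | 1.09 |

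The values are simulated. Solving the limiting Cox score equation by numerical integration instead agrees to within about 0.01. Follow-up of everyone to day 28 gives 1.00 throughout. With 250 per arm and a two-sided 5% test, the rejection rate is 4 to 5% in the 4.5 h and 10% rows and 4 to 7% in the 25% row. For 25% earlier at SD 1 and 2, varying mortality and length of stay as above gives about 1.07 to 1.11.

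**4. Deaths that are not counted.** At SD 0 this has a closed form:
- a = −ln(0.75)/672 = 0.000428 per hour
- b = ln(2)/96 = 0.00722 per hour
- share dying before discharge = a/(a + b) = 5.6%

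At SD 1 and 2 the simulated shares are 11.5% and 18.2%. Against 25% dead by day 28, the fractions counted are 5.6/25 = 22%, 11.5/25 = 46% and 18.2/25 = 73%. In a standard arm of 250, that is about 14, 29 and 46 deaths instead of about 63.

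**5. A true benefit.** If hTEE multiplies each patient's death hazard by 0.75 (SD 1):

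| Analysis | Hazard ratio | Power |
|---|---|---|
| Follow-up to day 28 | 0.78 | 26% |
| Censored at discharge, same timing | 0.77 | 15% |
| Censored at discharge, hTEE 25% earlier | 0.84 | 9% |

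**6. The date of death.** Dating deaths 6 h earlier on average moves the hazard ratio by at most 0.001 with follow-up to day 28. With censoring at discharge it moves by about 0.01 (for example 1.089 to 1.082 at SD 1).

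**The case against.** The strongest reply is that 9.9 makes loss to follow-up the condition, and discharge is only an example tied to the primary endpoint. Carried over to death, the rule could simply mean censoring when vital status is no longer known, which is standard. This reading is tenable. But the SAP names discharge as its instance of loss and nowhere describes vital status after discharge, so the softer reading cannot be taken as the stated one.

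It can also be said that death before discharge matches the scope of the endpoint that was replaced, and that the cause-specific hazard ratio is valid for it. Both are true. The endpoint should then carry that name. How long vital status was followed may also stand in the protocol, which is not at hand. However, the SAP introduced this endpoint as a deviation from the protocol, so its horizon and censoring rule belong in the SAP.

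The objection on size largely stands. The only scenario tied to a figure in the SAP, 4.5 h, gives 1.00 to 1.02. The 25% scenario needs 24 h off the stay, more than five times that saving (24/4.5 = 5.3), and the 25% in 4.2 refers to shock, not to length of stay. The share of deaths lost depends heavily on the assumed severity spread and on constant hazards. Power is low even with full follow-up to day 28.

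The dating rule is at least consistent between the two places where it is used. What is missing is a date for deaths that it does not cover.

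**Conclusion.** The point holds as a minor one. SAP 9.9 extends to time to death a rule suited to the primary outcome, 9.5.1 sets no horizon, and 7.3 leaves some deaths without a date. On the plain reading the result is a cause-specific hazard ratio for death before discharge. That is valid as such, but it is not a measure of mortality over a defined period.

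A reader might infer that the SAP definitely censors deaths at discharge, or that its mortality result will be seriously biased. The document supports neither. The wording allows a second reading. Bias needs both a severity link and a difference in discharge timing, and on the assumed inputs it is 0 to 3% on the hazard ratio in moderate cases and about 5 to 10% with discharge 25% earlier. Omitted deaths are the larger loss, but their number cannot be fixed from the SAP.

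A reader might also infer from 7.3 that the event has become discontinuation of therapy. It is still death, dated earlier, with almost no effect on the hazard ratio. The effect on the primary analysis is slight: a Fine-Gray model keeps patients with the competing event in the risk set, so only the missing date rule matters there.

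**What to change.** - **9.9:** exempt time to death, so that patients discharged alive stay at risk to the stated horizon or to their last known vital status.
- **9.5.1:** state one horizon for time to death, for example 28 days, as far as vital status was collected.
- **7.3:** derive time to death from the actual date and time of death. For the competing event of the primary outcome, state the date to use when a patient dies without discontinuation of therapy.
- **If vital status was collected only in hospital:** name the endpoint in-hospital death, treat discharge alive as a competing event, say that this estimates the risk of in-hospital death, and report in-hospital deaths by arm beside the hazard ratio.

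The cost is a few sentences and the re-derivation of one variable. No new type of model is needed, and hospital deaths are already an outcome in 6.3. Those descriptive counts alone do not settle the matter, because they too stop at discharge.

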#### 6.2. Secondary endpoints

• Time to death

CTU Bern	Statistical Analysis Plan ImaCorII	Date effective:	2018-04-24	
	Based on CS_STA_TEM-11_SAPtemplate_v01			Page 8 I 16

- Time to resolution of clinical signs of hypoperfusion as a composite of capillary refilling time < three seconds, urine output > 0.5 mL/kg/h for at least 4 hours, and blood lactate < 2 mmol/L.
- Use of conventional hemodynamic monitoring (3 binary endpoints):
  - o pulmonary artery catheter (yes/no),
  - o central venous catheter (yes/no),
  - conventional echocardiography (yes/no)
- Occurrence of adverse events assumed to be due to prolonged hemodynamic impairment and treatment with vasopressors/inotropes (as binary yes/no outcomes):
  - cardiac arrhythmias: non sustained ventricular tachycardia (≥ 4 beats), sustained ventricular tachycardia, ventricular fibrillation, atrial fibrillation, atrial flutter, other supraventricular tachycardia, new onset AV block (I/II/III), or asystole,
  - Excessive vasoconstriction: occurrence of acute myocardial infarction, skin necrosis, or secondary bowel or limb ischemia or stroke,
  - Secondary infections (catheter related infections, VAP, new onset of sepsis).

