#### 6.4. Safety endpoints (specific for use of hTEE only)

Occurrence of complications potentially attributed to the use of hTEE

- o Oral, pharyngeal, esophageal or gastrointestinal bleeding or injury
- Need for additional sedation and/or muscle relaxants for hTEE probe placement and hTEE assessment

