#### 7.2. Data validation

All variables used in the analysis, including the derived variables, will be checked for missing values, outliers, and inconsistencies and queried.

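### As worded, SAP 9.9 counts a blank hTEE complication field as no complication, and 9.7 does not require the number of blanks to be shown (minor)

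*SAP*

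**What the plan says.** - **Missing data (SAP 9.9).** Time-to-event outcomes are censored at loss to follow-up. For binary data the rule is "Missing binary data will be assumed as being absent". Continuous outcomes that are only described use available cases. The binary rule is not limited to efficacy and has no exception for safety.
- **Safety endpoints (6.4).** Two kinds of complication are listed, specific to hTEE: "Oral, pharyngeal, esophageal or gastrointestinal bleeding or injury" and "Need for additional sedation and/or muscle relaxants for hTEE probe placement and hTEE assessment". They serve the secondary objective in 3.2.
- **Safety reporting (9.7).** Counts and percentages are laid out for SAEs. For the rest, "All other information collected (e.g., severity or relationship to study treatment) will be tabulated and listed as appropriate". The section also states "Only SAEs that might be treatment related were collected and will be reported".
- **Data validation (7.2).** "All variables used in the analysis, including the derived variables, will be checked for missing values, outliers, and inconsistencies and queried".
- **Derivations (7.3).** Derivations are given for the primary, secondary and further endpoints, but none for the 6.4 endpoints.

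**The concern.** A complication that either occurred or did not is a binary item for each patient, even though 6.4 does not label it so. Section 9.9 is the only place in the SAP with a rule for missing binary items, and its wording covers all of them.

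If the form asks the question with an explicit yes/no field, a blank means that the answer is unknown. Turning unknown into no favours the device, which is the wrong direction for a safety endpoint. The 6.4 endpoints exist only for hTEE, so no control arm has the same understatement to set against it.

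The queries in 7.2 reduce the number of blanks but do not require the remainder to be reported. Under 7.1 the database has no built-in checks, so nothing stops a blank at entry. In the resulting table a reader could not separate a recorded no from an empty field. At stake is how far the descriptive complication rate for the probe can be interpreted, and nothing beyond that.

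**Working it through.** The SAP gives no complication rate and no number of blank fields, so there is no figure of its own to reproduce. The check has two parts.

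**1. Which rule governs a blank 6.4 field?**

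- 9.9, time-to-event rule: does not apply to an occurrence item.
- 9.9, continuous rule: does not apply.
- 9.9, binary rule: applies on its plain wording.
- 7.2: acts before analysis and is silent on what stays blank.
- 7.3: silent on 6.4.
- 9.7: its general sentence on other information permits a row for missing values but does not require one.

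The only rule that fits is therefore the one that sets the blank to absent.

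**2. How much could it move the rate?**

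Inputs from 4.2: 125 patients per group and two hTEE groups, so N = 2 × 125 = 250 planned. Without the drop-out allowance, N = 458/2 = 229. Let x be the recorded events and b the blanks.

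- Rate under 9.9: x/N.
- Rate among recorded values: x/(N − b), which is never lower than x/N.
- With explicit yes/no fields, the true rate lies between x/N and (x + b)/N. Each blank widens this range by 1/N: 1/250 = 0.40 percentage points, or 1/229 = 0.44.
- If blanks are unrelated to events and a share m is blank, the expected rate under 9.9 is p(1 − m) for a true rate p. The relative understatement is m.

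*Illustration only.* The one data-loss figure in the SAP is the 10% drop-out allowance in 4.2. It is not a rate of blank fields. Borrowing it gives b = 0.10 × 250 = 25. The event counts are assumptions, and the upper limits are those of exact (Clopper-Pearson) 95% intervals.

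| Recorded events | Under 9.9 | Recorded values only | Upper bound, every blank an event |
|---|---|---|---|
| 0 | 0/250 (upper limit 1.5%) | 0/225 (upper limit 1.6%) | 25/250 = 10% |
| 5 | 5/250 = 2.0% | 5/225 = 2.2% | 30/250 = 12% |

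With b = 5 (assumption) and no recorded events, the upper bound is 5/250 = 2.0%.

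*Blanks related to events (assumption).* Suppose the true rate is 5%, 10% of fields are blank, and events are three times as likely where the field is blank. The rate among recorded values is 0.05/(0.9 + 3 × 0.1) = 0.05/1.2 = 4.2%, and 9.9 reports 4.2% × 0.9 = 3.75%. Recorded values alone are then also too low, so the number missing has to stand beside the rate.

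**The case against.** **Scope.** The reach of 9.9 to 6.4 is inferred. Elsewhere the SAP uses the word binary only for the 6.2 endpoints (in sections 2 and 6.2) and for their models, as in "Binary outcomes will be analysed using logistic regression". Section 6.4 speaks of occurrence and prints no yes/no label. The authors may have had only the 6.2 outcomes in mind. This stands as a possible reading. On it, however, the 6.4 endpoints have no missing-data rule, and the same addition settles the matter.

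**Recording.** If complications were entered only when they happened, an empty entry means none and 9.9 gives the right answer. The sentence in 9.7 on which SAEs were collected hints at such recording, although it concerns SAEs. The form is not shown. This objection stands in full, and it is why the point holds only for explicit yes/no fields.

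**Existing safeguards.** Queries under 7.2 will remove some blanks, and 9.7 leaves room for a row of missing counts. Both are true, but neither makes reporting of the remainder a requirement.

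**Size.** Even at a borrowed 10% blank, the rate moves only from 2.0% to 2.2%. This is right. A reader might infer from the 10% and 12% figures that the plan could hide a complication rate of that order. The SAP does not support this: those figures assume both the share of blanks and that every blank was an event. They are bounds, not expectations.

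**Conclusion.** The point holds as a minor one. Followed as worded, the SAP counts an unknown hTEE complication as none and does not require the number of unknowns to be shown. Where the form has an explicit yes/no field, the reported rate on the secondary safety objective is lowered or left unchanged, never raised.

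The size cannot be determined from the SAP and is probably small, at most 0.40 percentage points per blank with 250 planned hTEE patients. The main loss is that the unknown share is invisible.

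The conclusion rests on two assumptions: that 9.9 means what it says about all binary data, and that the 6.4 items were captured as explicit fields, some of which stay blank after queries.

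A reader might go further and infer that the complication rate will certainly be wrong, or that the trial's main result is biased. Neither follows. The rule is correct if recording was only on occurrence, and the primary comparison is a time-to-event analysis that this rule does not touch.

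**What to change.** First look at the database to see how the 6.4 items were recorded. Then fix one rule:

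- **Explicit yes/no fields.** Add to 9.9: *This rule does not apply to the endpoints in 6.4.* Add to 9.7: *For each endpoint in 6.4 we report the number and percentage with the event among hTEE-monitored patients of the Safety Set with a recorded value, and the number of such patients with a missing value.*
- **Recorded only on occurrence.** Use all hTEE-monitored patients of the Safety Set as the denominator and say so in 9.7 and in the table. A denominator of recorded values would be meaningless here, because only events would have an entry.

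A row that counts every missing value as an event is optional, since the bound follows directly from the number missing. If shown, it should be labelled as a bound because it can exaggerate harm.

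The cost is two or three sentences and one small descriptive table. With explicit fields, the reported rate may be slightly higher and slightly less precise than under 9.9.
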